### Study Schema:

## RATIONALE & BACKGROUND

**STUDY RATIONALE:** The demonstrated ability of MCT to accurately assess tumor xenografts may establish it as a reliable technique for patient tumor stratification based on predicted response to therapy, which could enable a treatment selection based on the personal needs of an individual patient. This study is designed to assess MCT as an assay for predicting chemosensitivity to treatment with chemotherapy agents routinely used in the neoadjuvant and adjuvant treatment of bladder cancer. If positive, the results of this study will provide the basis for expanded clinical trials and use of MCT in therapy selection.

**BACKGROUND:** Live cell imaging has become the standard for high-content analysis and drug discovery applications. The most common assays on live cells include viability, proliferation and cytotoxicity assays as cellular physiology and function are measured responding to applied perturbations of xenobiotics. Cellular and tissue viability assays are typically measured using exogenous vital dyes as biomarkers of membrane integrity or cellular metabolic activity. However, dyes are invasive, potentially toxic, and often require fixing of the tissue or permeabilization of the membranes [1, 2]. Furthermore, the common format of high content analysis and flow cytometry requires isolated cells, or cells distributed on flat hard surfaces. Isolated cells lack many of the biologically-relevant intercellular connections and communications that are hallmarks of healthy tissue [3, 4], and flattened cells on plates have pathological shapes and anisotropic cellular adhesions [5].

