**EX VIVO CANCER CHEMOSENSITIVITY ANALYSIS** MCT was previously applied to study the efficacy of anti-mitotic drugs using multicellular tumor spheroids [40]. When applying MCT to tumor xenografts, it is also capable of showing a significantly different response between two cell lines under cisplatin. After applying the drug, the normalized standard deviation (NSD) value of the platinum-sensitive cell line (A2780) drops from 0.7 to 0.1 in 8

hours. In contrast, the NSD value of the platinum-resistant cell line (A2780-CP70) remains nearly constant (0.81 to 0.80) 9 hours after applying drug. The NSD value of normal mouse tissue attached to the tumor xenograft decreases only a little (0.6 to 0.52) compared with A2780. Fig. 2 shows the cisplatin drug response curves. The NSD value of each point is averaged over the entire target. The time between measurements is 24 minutes for A2780-CP70 and normal mouse tissue and is 12 minutes for A2780. The 20  $\mu\text{M}$  cisplatin was applied at time  $t = 0$ , and the measurements lasted 9 hours for A2780-CP70 and normal mouse tissue, and lasted 8 hours for A2780. At time=0, the aggressive cell line A2780-CP70 has the highest NSD and the normal mouse mesenterium tissue has lowest NSD (0.6). The NSD of the platinum-sensitive cell line A2780 lies in the middle: 0.7. After applying cisplatin, the NSD curve of A2780 drops immediately. The NSD value of the A2780-CP70 almost doesn't change.

[figure not shown]

Fig. 2 Motility metric (NSD) of ovarian cancer tumor xenografts responding to 20  $\mu\text{M}$  cisplatin. The x-axis is time (minute), the y-axis is NSD value. The sensitive tumor is A2780, while the insensitive tumor A2780-CP70. Both tumor tissues begin with higher motility than normal mouse tissue. The cisplatin was added at time  $t=0$ . The NSD of A2780 dropped very fast and after 8 hours it dropped to 0.1. The NSD of the insensitive tumor A2780-CP70 didn't change during 9 hour period. The NSD of normal mouse tissue dropped a little compared with the A2780.

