## MEASUREMENT OF EFFECT – MOTILITY CONTRAST TOMOGRAPHY

The foundational data structure that is obtained by MCT is a time-frequency spectrogram. This spectrogram captures how the Doppler frequencies of intracellular motion respond to the applied drug. This data structure is two-dimensional and can exhibit a variety of patterns that have been associated with mechanistic response of the tissue to the drug. To further improve the interpretation of the MCT results, numerous metrics have been developed that quantify the cellular response. These include: Backscatter brightness, NSD, change in NSD, dipole sine response, dipole cosine response, and quadrupole response. A further set of metrics, that are linearly dependent on the previous metrics, have more direct cellular mechanistic basis. These include: mitotic index, apoptotic index, necrotic index, metabolic activity, and membrane ruffling. These metrics are non-orthogonal, and a patient will often show strongly correlated responses among these metrics. Multiparameter logistic regression is performed on these metrics to provide a single-valued predictor of therapy response.

---

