## STATISTICAL CONSIDERATIONS

**STUDY DESIGN:** This is a non-randomized, multi-arm, multi-center, feasibility study, designed to examine the feasibility of using MCT as a chemosensitivity assay among bladder cancer patients by comparing ex-vivo MCT patterns consistent with chemotherapy response and resistance to confirmed pathological response or resistance as measured by Response Evaluation Criteria in Solid Tumors (RECIST) v1.1 criteria.

**DEFINITION OF PRIMARY OUTCOME ENDPOINT:** Feasibility is defined as a high statistical correlation between MCT-predicted response, and surgically confirmed response to neoadjuvant chemotherapy.

**ANALYSIS PLAN FOR PRIMARY OBJECTIVE:** The study will be considered successful, if a majority of specimens yield interpretable MCT results, and if MCT signatures are identified which demonstrate a high statistical correlation to confirmed patient response.

**EXPLORATORY ANALYSIS:** Due to the inadequate samples size, no formal analysis is planned. Descriptive analysis of the correlation between MCT parameters and clinical outcome measures will be performed.

**DETERMINATION OF SAMPLE SIZE:** A target sample size of 500 patients was selected for initial enrollment using the investigators' previous research experience to approximate the appropriate number needed to demonstrate the feasibility of this technique. It is anticipated that only 20-30% of enrolled patients will yield specimens evaluable for response. It is estimated that it will take approximately 6-12 months to complete accrual.

**EVALUATION FOR RESPONSE:** Participants who provide a bladder tumor specimen, have received at least one cycle of chemotherapy, and have had their disease re-evaluated upon surgical resection will be considered evaluable for response.

**REPLACEMENTS:** Participants who withdraw from the study prior to having the TURBT procedure or fail to complete at least one evaluation for response will be replaced. No reported data will be included for participants who are replaced.

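### The success rule does not require the MCT signature to be drug-induced or to come from the regimen the patient received

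*Protocol*

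**What the plan says.** Statistical Considerations sets two joint conditions. The first is "The study will be considered successful, if a majority of specimens yield interpretable MCT results"; the second is "if MCT signatures are identified which demonstrate a high statistical correlation to confirmed patient response". The primary outcome is worded in the same spirit: "Feasibility is defined as a high statistical correlation between MCT-predicted response, and surgically confirmed response to neoadjuvant chemotherapy". Neither sentence names a metric, a drug, a match between assay and treatment, or a comparison with the pre-drug state.

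The section on measurement of effect by MCT gives the candidate metrics. Six come first: "Backscatter brightness, NSD, change in NSD, dipole sine response, dipole cosine response, and quadrupole response". Five more are derived from them: "mitotic index, apoptotic index, necrotic index, metabolic activity, and membrane ruffling". All feed a logistic regression that yields one predictor.

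Drug Formulation and Procurement ranks three regimens for imaging and tests the lower-ranked ones only if enough tissue remains. The Chemotherapy Treatment Plan leaves the regimen given to routine care and the treating physician. Under Study Rationale, the protocol says that if the study is positive, "the results of this study will provide the basis for expanded clinical trials and use of MCT in therapy selection".

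**The concern.** The aim is a chemosensitivity assay: does the tumour's reaction to a drug outside the body foretell the patient's response to that drug? The success rule asks for less, namely that some MCT signature correlates with response.

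Two kinds of signature could meet the rule without answering the question. One is a feature of the tumour that is present whatever drug is applied and that goes with better or worse outcome. The other is a reaction to a regimen the patient never received. Either could be reported as chemosensitivity. A feature of the first kind cannot tell an oncologist which therapy to avoid, and that is the use the protocol has in view. A signature of the second kind has not been tested against the treatment it is said to predict.

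**Working it through.** The protocol gives no correlation threshold, significance level or effect size, so the point rests mainly on reading the sections together.

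**Step 1. Must the signature be drug-induced?** The rule does not say so. The metric list names brightness and NSD separately from change in NSD, so level metrics are candidates. Biopsy Sample Processing and Analysis provides a 2-4 hour baseline before drug is added, so pre-drug values will exist. No sentence says that they enter the predictor, and none says that they do not.

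**Step 2. Must the well match the treatment?**
- Imaging order is fixed: DDMVAC first, then gemcitabine with cisplatin, then CMV, as tissue allows (Drug Formulation and Procurement).
- The specimen is shipped for next-day delivery (Biopsy Sample Collection Parameters), whereas the recommended regimen is forwarded once it is known (Appendix B, item 3k). Imaging may therefore precede knowledge of the treatment.
- Treatment is at physician discretion, and an additional biologic agent is possible within a separate trial (Chemotherapy Treatment Plan).
- The definition of evaluable for response in Statistical Considerations needs a specimen, at least one cycle and re-evaluation at surgery. It does not need a well exposed to the regimen received.

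A patient with little tissue who is treated with the second or third regimen may thus have spectra for DDMVAC only, and still count.

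**Step 3. How many patients does this concern?** Enrolment is 500 and the evaluable share 20-30%:

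500 × 0.20 = 100 and 500 × 0.30 = 150.

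If a share m of these has a matched well, the usable number is 100m to 150m. The protocol gives no figure for m. As an illustration only, m = 0.5 would leave 50 to 75.

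**Step 4. What correlation could be seen at these sizes?** At an assumed two-sided 0.05, the smallest nominally significant correlation is |r| = t / √(n − 2 + t²).

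| n | t | smallest r |
|---|---|---|
| 50 | 2.011 | 0.279 |
| 75 | 1.993 | 0.227 |
| 100 | 1.984 | 0.197 |
| 150 | 1.976 | 0.160 |

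**Step 5. Would a drug-independent feature be visible, if there were one?** Assume that such a feature differs by d standard deviations between responders and non-responders, and that the response rate p is 0.2 to 0.6 (the range in the Project Summary). Then r = d√(p(1−p)) / √(1 + d²p(1−p)) and AUC = Φ(d/√2).

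| d (assumed) | r over p = 0.2 to 0.6 | AUC | nominally significant, simulated, n = 100 or 150 |
|---|---|---|---|
| 0.5 | 0.20 to 0.24 | 0.64 | 52-84% |
| 0.8 | 0.30 to 0.37 | 0.71 | 87% to nearly 100% |
| 1.2 | 0.43 to 0.51 | 0.80 | over 99% |

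The last column comes from 1,000 simulated studies per setting. This shows only that a moderate prognostic feature would be readily detected at the planned size. It does not show that one exists, or that such values of r would be called high.

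**The case against.** The best defence is that the rule should be read with its surroundings. Specific Aims and Statistical Considerations both speak of MCT patterns that fit response or resistance to chemotherapy, and the MCT section describes the spectrogram as tracking the reaction to the applied drug. The intent is clearly drug response. The study is one of feasibility, and expanded trials are the stated next step. The regimen given is recorded (Data and Record Keeping; Appendix B, item 4), so a statistical analysis plan, which is not shown, could match wells to patients.

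The intent stands, and so does the view that detailed metric definitions belong in an analysis plan. But the protocol itself fixes the success rule, and that rule does not carry the intent. The step to therapy selection is also the protocol's own claim.

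Four stronger readings are tempting and should be set aside.
- *That some of the six metrics are by definition drug-free.* The protocol does not define them so. In its xenograft example NSD is followed over time after cisplatin.
- *That the xenograft data already show baseline NSD sorting resistant from sensitive tumours.* The text does say "At time=0, the aggressive cell line A2780-CP70 has the highest NSD" (0.81, against 0.7 for the sensitive line). That is one tumour per line, and two tumours fall in the expected order half the time by chance. Normal mouse tissue had the lowest starting value, 0.6, yet fell only to 0.52.
- *That cisplatin in all three listed regimens makes a signature purely prognostic.* A reaction to cisplatin is a drug effect. The shared agent only limits discrimination between regimens, and single agents are imaged where tissue permits.
- *That the simulation proves the danger.* It assumes the difference that it then detects.

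**Conclusion.** The point holds as a fault in how the success rule is fixed. Followed to the letter, the plan could credit a drug-independent or regimen-mismatched signature as evidence of chemosensitivity and as support for choosing therapy. The interpretability condition does not guard against this, because it says nothing about drug effect.

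The size cannot be stated as a probability. It depends on whether baseline values are used, on the share of patients with a matched well, and on what counts as a high correlation, and the protocol gives none of these. What can be said is that up to 100 to 150 evaluable patients are affected by the missing match requirement. At that number, a prognostic feature with an assumed difference of 0.5 to 1.2 SD would reach nominal significance in 52% to over 99% of simulated studies. The conclusion does not depend on that simulation. It rests on the wording of the rule, the imaging order and the discretion over treatment. It should be put right before the success rule is applied.

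**What to change.** In Statistical Considerations, under the analysis plan for the primary objective:

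1. Base the success correlation on drug-induced MCT metrics, meaning post-drug change from the specimen's own baseline, in wells exposed to the regimen the patient received.
2. Report how many evaluable patients have a matched well, and say how patients given an agent that was not imaged are classified.
3. In the same patients, report the correlation using pre-drug baseline metrics only. Describe the result as chemosensitivity only if the drug-induced metrics add to baseline; otherwise describe it as prognostic.
4. Report the correlation for regimens or single agents not received, where imaged, as description only and not as a condition of success. These wells depend on spare tissue, so the subset is unknown, and a formal comparison of two correlated signatures would often lack power.

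The baseline spectra and the regimen given are already collected, so no patient procedure or treatment changes. The cost is real: where no matched well exists, the usable number falls below 100 to 150, and success becomes harder to claim. If half the patients were matched (an assumption), the smallest nominally significant correlation would rise from 0.160-0.197 to 0.227-0.279.

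### The protocol calls its sample about right for demonstrating feasibility, yet inadequate for formal analysis of the correlation that defines feasibility

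*Protocol*

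**What the plan says.** All but one of the statements at issue stand in the protocol's Statistical Considerations section.

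- The primary outcome is fixed in these terms: "Feasibility is defined as a high statistical correlation between MCT-predicted response, and surgically confirmed response to neoadjuvant chemotherapy".
- The plan for the primary objective makes success depend on two things. A majority of specimens must give interpretable MCT results, and the second condition is met "if MCT signatures are identified which demonstrate a high statistical correlation to confirmed patient response".
- The paragraph that deals with exploratory work says: "Due to the inadequate samples size, no formal analysis is planned". All that it offers in place of a formal analysis is this: "Descriptive analysis of the correlation between MCT parameters and clinical outcome measures will be performed".
- The paragraph on the number of patients rests the enrolment target of 500 on what the investigators learned from earlier work, and gives its purpose as "to approximate the appropriate number needed to demonstrate the feasibility of this technique". The usable share is put much lower: "It is anticipated that only 20-30% of enrolled patients will yield specimens evaluable for response".

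The section on measurement of effect by MCT describes how the predictor is built: "Multiparameter logistic regression is performed on these metrics to provide a single-valued predictor of therapy response".

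**The concern.** Feasibility is defined as the MCT-response correlation, so a sample suited to demonstrating feasibility should be suited to demonstrating that correlation. The same section calls the sample inadequate and leaves the correlation between MCT and outcome to description. It names no estimate, interval or test for that association under the primary objective either.

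The Project Summary says that a high predictive value will provide the basis for larger trials and commercialization. A positive result would rest on a correlation with no planned statement of its uncertainty, from a sample that the protocol itself calls inadequate. A disappointing result could be set aside by pointing to the same sentence.

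**Working it through.** **1. The plan's own figure.** The 500 cannot be reproduced. The protocol gives no error rate, power, effect size, threshold for a high correlation, or precision target. Only the evaluable number can be derived: 500 × 0.20 = 100 and 500 × 0.30 = 150.

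**2. The statements side by side.**

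| Paragraph | What it implies |
|---|---|
| Primary outcome endpoint | Feasibility is the correlation of MCT-predicted with surgically confirmed response |
| Primary objective | That correlation is one of two success conditions; no analysis of it is named |
| Sample size | 500 is roughly the right number to demonstrate feasibility |
| Exploratory analysis | The sample is inadequate; no formal analysis; the MCT-outcome correlation is described |

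The first and third rows make the sample suitable for the correlation. The fourth says it is not, and offers the only analysis of that association in the section.

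**3. What precision the sample could give (illustration only).** The assumptions are an AUC of 0.80, which is not in the protocol; 20-60% responders, the general chemotherapy range in the Project Summary and not a figure for this cohort; and a predictor fixed before the data are seen. The Hanley-McNeil standard error is

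SE² = [A(1−A) + (n₁−1)(Q₁−A²) + (n₂−1)(Q₂−A²)] / (n₁n₂), with Q₁ = A/(2−A) and Q₂ = 2A²/(1+A).

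At A = 0.80: Q₁ = 0.6667, Q₂ = 0.7111, Q₁−A² = 0.0267, Q₂−A² = 0.0711.

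- n = 100, 20 responders: SE² = (0.16 + 19×0.0267 + 79×0.0711)/1600 = 0.00393; half-width 1.96 × 0.0627 = 0.123.
- n = 100, 60 responders: half-width 0.085.
- n = 150, 30 responders: half-width 0.100.
- n = 150, 90 responders: SE² = (0.16 + 89×0.0267 + 59×0.0711)/5400 = 0.00125; half-width 1.96 × 0.0353 = 0.069.

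On the correlation scale, with an assumed r of 0.5 and Fisher's z (SE = 1/√(n−3)), the 95% interval is 0.34-0.63 at n = 100 and 0.37-0.61 at n = 150.

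**4. Fewer patients may carry both results.** The definition under Evaluation for Response does not require an interpretable MCT result, and the success rule asks only for a majority of specimens. If that majority is applied to the evaluable patients (an assumption), the smallest numbers are 51 of 100 and 76 of 150. At n = 51 with 10 responders, SE² = (0.16 + 9×0.0267 + 40×0.0711)/410 = 0.0079, so the half-width is 1.96 × 0.089 = 0.174.

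**5. The predictor may be fitted to the same patients.** The success rule speaks of signatures being identified, and the protocol does not say that the regression was fixed beforehand. It names 6 base metrics and 5 more that depend linearly on them. With 20 responders of 100, the smaller outcome group gives 20/11 = 1.8 patients per metric, or 20/6 = 3.3 per base metric. With 75 of 150 it gives 75/11 = 6.8, or 75/6 = 12.5. In simulation, six pure-noise metrics fitted by logistic regression and judged on the same patients give a mean apparent AUC of 0.61-0.67 at n = 100-150, where the true value is 0.50. The intervals in steps 3 and 4 do not allow for this.

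**The case against.** **The heading.** The sentence stands under Exploratory Analysis, apart from the primary objective. It speaks of MCT parameters and outcome measures in the plural, whereas the primary endpoint compares one predicted response with one confirmed response. It may therefore be meant only for secondary looks. That reading is possible and the fix adopts it, but the text does not secure it. The primary paragraph names no analysis, and the reason given, an inadequate sample, would apply to the primary association as well.

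**Feasibility studies.** A sample can be enough to see whether an assay works and too small for formal inference. That would be a full answer if feasibility meant interpretable specimens alone. Here it is defined as the correlation.

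**The SAP.** Interval methods are commonly left to the SAP, and no passage forbids an interval. This stands in part: a reader might infer that the protocol commits to a bare point estimate, and it does not. It simply plans no formal analysis. A SAP that added one could do so only by departing from this sentence or by narrowing it.

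**The logistic regression.** A reader might take the regression as a further contradiction of having no formal analysis. It is not, because it is described as building a score and not as a planned inference.

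**The word inadequate.** A reader might infer from step 3 that 100-150 patients are plainly enough and the word is wrong. The documents do not support that. Steps 4 and 5 show conditions under which it would be fair, and splitting by the three listed regimens would thin the data further.

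**Conclusion.** The protocol contradicts itself on its primary claim: the sample is approximately right for demonstrating a correlation and, in the same section, inadequate for formally analysing it. This follows from the text and needs none of the illustrative numbers.

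The effect is limited to one of the two success conditions. Success also requires that most specimens be interpretable, so it would be wrong to say that it rests on the association alone.

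The illustrated 95% half-width for the AUC is 0.07-0.12 at 100-150 patients and up to about 0.17 at 51. It depends on an assumed AUC of 0.80, a response range not specific to this cohort, and a predictor fixed in advance. These figures show that an interval can be reported and why its width should be stated. They do not show that the sample is adequate.

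**What to change.** 1. In Exploratory Analysis, limit the statement that no formal analysis is planned to analyses that are truly exploratory: individual MCT parameters, other outcomes and single regimens. Keep the caution about sample size for those.
2. In Analysis Plan for Primary Objective, state that the association between the single-valued MCT predictor and surgically confirmed response is the primary analysis, reported with a 95% confidence interval. If the predictor is fitted to the same patients, require the estimate and interval to be corrected for optimism, for example by cross-validation or bootstrap.
3. In Determination of Sample Size, give the expected interval width at the number of patients with both an interpretable MCT result and an evaluable response. This may be well below 100-150.

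The cost is a few sentences and a little more analysis work, with no new patients, procedures or data. The stated precision may also look less favourable than the sponsor would like.
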